The subject population in this study will be 50 male and female O/O/O Veterans with mental health conditions and cognitive impairment served by the Aspire Center. It is anticipated that we will need to enroll and test 200 participants to end up with 98 who have cognitive impairment. We anticipate the top four mental health conditions to be PTSD, depression, history of substance use disorder, and history of TBI. Our inclusion criteria were selected in order to increase generalizability to other treatment-seeking homeless O/O/O Veterans with cognitive impairment. Participants will be men and women of any race/ethnicity, aged 18-55 years (which will represent the vast majority of O/O/O Veterans, but not introduce age-related dementing disorders as a confound). Complete inclusion/exclusion criteria are as follows:

Inclusion Criteria:

- 1) Male or female, any race/ethnicity, and age 18-55
- 2) Meets criteria for Aspire Center program entry
 - a) O/O/O Veteran
 - b) presence of at least one DSM-V mental health condition
 - c) does not meet criteria for substance use disorder for 28 days prior to admission
 - d) homeless or unstably housed (per HEARTH Act definition; HUD, 2011b)
 - e) not a sex offender or violent offender
 - f) capable of performing activities of daily living and transfers
 - g) not judged by a clinician to be at current risk to self or others
- 3) Has cognitive impairment in at least one cognitive domain (i.e., T-score < 40)
- 4) Able to speak and read English
- 5) Capable of and willing to provide signed informed consent

Exclusion Criteria:

None

Although it is recognized that the effects of chronic alcohol abuse can last longer than 28 days, the number of individuals in the study with recent alcohol abuse should be equally allocated across the two treatment groups by virtue of the power of randomization. In the unlikely event in a study this size that the treatment groups differ in this regard, alcohol history may be used as a covariate in the analyses.

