All participants will provide voluntary informed consent (we will not enroll participants who require surrogate consent). All potential participants who meet the inclusion and exclusion criteria above will be invited to participate; we anticipate that about 50% of the Aspire Center residents will meet these criteria and choose to participate, based on our prior research experience with homeless individuals (Vella et al., 2014). Those who enroll but turn out not to have cognitive impairment will end their research participation and will not participate in the randomized controlled trial; these participants will be replaced until the target enrollment of 98 participants is reached. Potential participants will meet with a project staff member, who will describe the study and answer any questions. In all cases, fully informed consent will be obtained. [name] will be directly available to answer any questions raised by a potential participant. A copy of the consent form, which includes a description of the study, will be provided to all subjects. The study population is at risk for diminished capacity to consent to research by virtue of their expected cognitive impairment, so participants will be assessed for capacity to consent for this study with a post-consent quiz, which will include questions about the purpose of the study, types of assessments, number of groups, voluntariness, and the ability to withdraw at any time without penalty. Potential participants will be given three chances to answer each question correctly, with the correct information provided in the event the individual answers incorrectly. We have used this procedure in prior studies to ensure decisional capacity. Four out of the five questions are open-ended in order to reduce the chance that the consenter could inadvertently reveal the right answer.

Inclusion of Women, Ethnic Minorities, and Children

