We have selected measures based on 4 criteria: 1) importance for assessing constructs in our theoretical model, 2) brevity (to reduce subject burden), 3) reliability, and 4) demonstrated validity.

Subject Characterization Measures

Measures of demographics, residential and vocational history, and history of alcohol and substance abuse will be administered by Aspire Center staff as part of the routine clinical intake process at program entry (Table 2). Subject characterization measures we will add (Table 3) include the Warrior Administered Retrospective Casualty Assessment Tool (WARCAT; Terrio et al., 2009), a short, structured interview of TBI history that allows for diagnosis of mild, moderate, or severe TBI based on the American Congress of Rehabilitation Medicine criteria, and the Wide Range Achievement Test-4 (Wilkinson et al., 2006) Reading subtest, which provides an estimate of premorbid IQ by measuring ability to read non-phonetically spelled English words.

Table 2. Measures Administered during Aspire Center Intake (no additional subject burden)

Measure	Construct Assessed
Demographic Form	Age, sex, education, race/ethnicity, marital status, service connection, medications prescribed
Residential Timeline Follow-Back (Tsemberis et al., 2007)	Residential history (number of days homeless, unstably housed, in an institution, or housed in the past 6 months)

Alcohol Use Disorders Identification Test (Saunders et al., 1993)	Alcohol use history
Drug Abuse Screening Test (Skinner, 1982)	Substance use history

Study Measures

Additional study measures are listed in Table 3 and further described below. Time required for these measures will be about 2 hours, 15 minutes, and breaks will be provided as needed by participants. We will administer a comprehensive, standardized battery at all four time points, including the following:

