Performance validity will be measured with the Test of Memory Malingering (TOMM; Tombaugh, 1997), a commonly-used validity measure. Sub-optimal effort (i.e., scores below standard cut-offs) is associated with significantly poorer neuropsychological test battery performance, thus making impaired scores uninterpretable. If a Veteran performs below standard cut-offs, indicating non-effortful performance, he/she will be excluded from the remainder of the study, because the cognitive test results will not be interpretable. We expect that the rate of non-effortful performance in this sample will be < 10%, based on estimates of effort-test performance in our archival database of over 400 O/O/O Veterans with TBI who have been referred for neuropsychological assessment. About 12% of that sample had invalid test results, but we expect our rate to be lower, given that not all Aspire Center residents will have sustained a TBI and the assessments will be administered in a research context rather than for clinical purposes.

Processing speed, attention/vigilance, working memory, verbal and visual learning, reasoning and problem-solving, and social cognition will be measured with the MATRICS Consensus Cognitive Battery (MCCB; Nuechterlein et al., 2008; see Table 4), a 60-minute battery of tests funded by an NIH initiative and developed through systematic selection and psychometric evaluation of the tests. Each test's relationship to functional outcomes, high test-retest reliability, and low practice effects were considered paramount, as the MCCB was designed to be used to detect clinically meaningful cognitive change (Nuechterlein et al., 2008). The four-week test-retest intraclass correlation coefficient for the MCCB composite score is .90. Of the ten MCCB tests, three (those measuring verbal learning, visual learning, and problem-solving) have alternate forms that will be used for assessment sessions after the baseline assessment; the other tests have very low practice effects.

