The related constructs of disability, community integration, and quality of life will be assessed by the World Health Organization Disability Assessment Scale 2.0 (WHODAS 2.0; WHO, 2012), the WHOQOL-BREF (WHO, 1998) and the Community Reintegration of Service Members-Computer Adaptive Test (CRIS-CAT; Resnik et al., 2012), three brief, well-validated measures. The CRIS-CAT is a self-administered computer adaptive test specifically designed for military and Veteran populations; the authors have obtained permission for the CRIS-CAT to be available on VA computers.

We will also measure heart rate variability via a brief (5 minute) heart rate monitor test. Heart rate variability may be a predictor of outcome in this population.

Table 3. Study Measures

Measure	Construct Assessed	Time (min)
Warrior Administered Retrospective Casualty Assessment Tool	History of TBI	5 (baseline only)
Wide Range Achievement Test-4 Reading	Reading ability (premorbid IQ estimate)	5 (baseline only)
Test of Memory Malingering	Test-taking effort	10
MATRICS Consensus Cognitive Battery (see Table 4)	Neuropsychological functioning (see domains in Table 4)	60
Additional tests: D-KEFS Verbal Fluency, Color-Word Interference, BEAM, heart rate variability	Executive functioning tests measuring cognitive flexibility, inhibition, attention; heart rate variability	25
Trail Making Test, Part B	Additional executive functioning test	5
UCSD Performance-Based Skills Assessment-Brief	Functional capacity	10
Cognitive Problems and Strategies Assessment*	Self-reported cognitive problems and strategy use	5
PTSD Checklist-5*	PTSD symptom severity	3
Patient Health Questionnaire-9*	Depressive symptom severity	2
Neurobehavioral Symptom Inventory*	Neurobehavioral symptom severity	3
Insomnia Severity Index*	Insomnia symptom severity	2
WHODAS 2.0*	Disability and community integration	7
WHOQOL-BREF*	Quality of life	2
Community Reintegration of Servicemembers-Computer Adaptive Test	Community reintegration	10

Note that assessments marked with * above will be administered via eScreening.

The electronic screening packet (i.e., the tablet and software) was developed by "Triple i", a Transformation Twenty One Total Technology (T4) prime contractor, and approved for use by the VASDHS ISO ([name]) and CIO ([name]) and Network 22 CIO ([name]) on November 21, 2012 (see attached Risk Based Decision Memo; note: although the RBDM diagrams VistA connectivity, this protocol does not utilize this feature).

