Statistical analyses: These potential moderators will be entered into the mixed effects models from H1a (GDS, UPSA-B, WHODAS 2.0) and the ANOVA models from H1b (proportion of months housed, proportion of months engaged in productive activity [work or school], and proportion of VA healthcare appointments attended during the 1-year follow up period) to assess interactions between the moderators and the independent variable (treatment group).

Section 9.8 Questionnaires & Surveys

9.8) Provide the name and a reference for questionnaires/surveys that are standard or identify them here and attach a copy of the questionnaire/survey. Questionnaires or surveys that are not clinical standard references must be uploaded. Reference the help link for additional information related to surveys administered to VA personnel and approved platforms for web-based surveys.

1. Performance validity will be measured with the Test of Memory Malingering (TOMM; Tombaugh, 1997), a commonly-used validity measure. Sub-optimal effort (i.e., scores below standard cut-offs) is associated with significantly poorer neuropsychological test battery performance, thus making impaired scores uninterpretable. If a Veteran performs below standard cut-offs, indicating non-effortful performance, he/she will be excluded from the remainder of the study, because the cognitive test results will not be interpretable. We expect that the rate of non-effortful performance in this sample will be <10%, based on estimates of effort-test performance in our archival database of over 400 O/O/O Veterans with TBI who have been referred for neuropsychological assessment. About 12% of that sample had invalid test results, but we expect our rate to be lower, given that not all Aspire Center residents will have sustained a TBI and the assessments will be administered in a research context rather than for clinical purposes.

2. Processing speed, attention/vigilance, working memory, verbal and visual learning, reasoning and problem-solving, and social cognition will be measured with the MATRICS Consensus Cognitive Battery (MCCB; Nuechterlein et al., 2008; see Table 4), a 60-minute battery of tests funded by an NIH initiative and developed through systematic selection and psychometric evaluation of the tests. Each test's relationship to functional outcomes, high test-retest

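### The effort-test (TOMM) exclusion names no visit: a baseline screen is probably meant, but read literally it ends follow-up for randomised participants, and the eligibility and replacement rules omit it

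*Combined protocol and SAP*

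**What the plan says.** Everything here is in the combined protocol and SAP.

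- **The rule.** Section 9 (Study Measures) and Section 9.8 carry the same sentence: "If a Veteran performs below standard cut-offs, indicating non-effortful performance, he/she will be excluded from the remainder of the study". Neither names a visit. The clause with its reason reads "he/she will be excluded from the remainder of the study, because the cognitive test results will not be interpretable"; the sentence before it says that low effort makes impaired scores uninterpretable.
- **When the TOMM is given.** Study Measures introduces the tests with "We will administer a comprehensive, standardized battery at all four time points, including the following", and the TOMM is the first one described. In Table 3 the time entries for two other tests (TBI history interview, reading test) read "5 (baseline only", closing bracket omitted here; the TOMM row has no such tag.
- **Order of events.** Under Procedure, randomisation comes after the baseline assessment.
- **Expected failures.** One figure is given for the sample, not one per visit: "We expect that the rate of non-effortful performance in this sample will be < 10" per cent. The archival comparison figure is about 12%.
- **Eligibility.** Sections 9 and 10 each present a list described as complete. Neither has a TOMM criterion, and both give no exclusion criteria.
- **Replacement.** For enrolled people found not to be impaired, "these participants will be replaced until the target enrollment of 98 participants is reached". The screening estimate is likewise framed by impairment: "we will need to enroll and test 200 participants to end up with 98 who have cognitive impairment".
- **Analysis.** H1a uses mixed models on all randomised participants with baseline and at least one later evaluation. It retains those terminated early and adds pattern-mixture models. H1b compares proportions of months by ANOVA, using whatever months are available.

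**The concern.** The rule can be applied in two ways, and the text does not choose between them. As a baseline screen it is an ordinary eligibility check. As a rule for every visit it removes randomised participants on a measure taken after treatment began, so the groups compared later may no longer be those formed by randomisation.

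The literal rule also reaches further than its reason. Uninterpretable cognitive scores do not explain why housing and work/school calls should stop. Those calls begin at programme discharge, and stays average 3-6 months, so someone removed at week 5 or 10 would usually have no call data at all. Attendance comes from the medical record. Housing has a medical-record fallback, though it is written for Veterans who cannot be reached. Work/school has none.

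Separately, staff working from the eligibility lists would not find the criterion, and the plan does not say whether a baseline failure is replaced or allowed for in the 200 to be tested.

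**Working it through.** **1. Do the documents settle the visit?** The all-visits introduction and the untagged Table 3 row point one way; the rationale and the single failure rate point the other. Battery time does not decide it. Table 3 sums to 154 minutes in full, 144 without the two tagged tests, and 134 without the TOMM as well. The text says "Time required for these measures will be about 2 hours, 15 minutes", that is, about 135. This lies nearest 134, but the word about allows 144, and 134 would mean the TOMM is not repeated at all, contrary to the introduction. By contrast, Section 10 does say that unimpaired participants leave after baseline.

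**2. The plan's own figures.** 98 × 0.80 = 78.4, matching the stated 78. For H1b, 39 per group and an effect size of 0.64 at two-sided 0.05 (alpha assumed; not stated beside the figure) give power 0.807 by the normal approximation and 0.797 by noncentral t. The stated 0.80 reproduces.

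**3. How many randomised participants could be affected?** No post-baseline failure rate is given, so I assume 2-5% at each of weeks 5, 10 and 15 (the analysis-plan visits; Procedure gives 3, 12 and 15 weeks, which does not change the point).

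- 98 × [1 − (1 − 0.02)³] = 98 × 0.059 = 5.8
- 98 × [1 − (1 − 0.05)³] = 98 × 0.143 = 14.0
- Weeks 5 and 10 only: 98 × [1 − (1 − f)²] = 3.9 to 9.6

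If all these losses came on top of the 20% attrition (not stated) and left no call data, work/school would have 78.4 × (1 − 0.059) = 73.8 or 78.4 × (1 − 0.143) = 67.2 participants. Power at 0.64 would be about 0.79 or 0.75 (normal approximation).

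**4. How large could the bias be?** These are illustrative simulations with no true effect: 1,000,000 per arm, four visits, compound symmetry with correlation 0.5 or 0.8, equal failure hazard at the three later visits, and maximum likelihood with saturated arm-by-time means. The H1b outcome is assumed to correlate r = 0.3-0.5 with stable cognition. The first two figures in each row are for correlation 0.5 and 0.8.

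| Cumulative failure, by arm | H1a week 15, failed visit's scores dropped (SD) | H1b (SD) |
|---|---|---|
| 5% v 12%, both from below-median scores | 0.023 / 0.011 | 0.045r / 0.059r |
| 12% v 12%, one arm at random, the other from below-median scores | 0.038 / 0.019 | 0.075r / 0.096r |
| 10% v 10%, same mechanism | within 0.001 | within 0.001 |

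The largest H1b value is 0.096 × 0.5 = 0.048. Raising the second case to 14.3%, the upper figure in step 3, gives about 0.045 for H1a and 0.055 for H1b. If the failed visit's scores are kept, H1a bias is about zero in every case.

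**5. How many must be tested at baseline?** Impaired share: 98/200 = 0.49 from the screening estimate, or about 0.50 from Section 10.

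- Failure unrelated to impairment (assumption), 10%: 98/(0.50 × 0.90) = 218; 98/(0.49 × 0.90) = 222
- The same at 12%: 98/(0.50 × 0.88) = 223; 98/(0.49 × 0.88) = 227
- A 10% failure rate wholly among the impaired (assumption): 98/(0.49 − 0.10) = 251

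The last case matters because the protocol itself links low effort to poorer battery performance.

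**The case against.** The best reply is that this is a baseline screen with a phrase missing. Administering a test at four visits is not the same as applying an exclusion at four visits. The rationale is about impaired scores, and impairment is an entry criterion. One failure rate is given, as for a one-time check. The H1a analysis set has no TOMM condition, the 20% attrition has no TOMM component, and attendance is said not to be subject to missing data. That evidence stands, and it makes harm less likely. It does not remove the point, because no sentence limits the rule to baseline.

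A second reply is that the analysis already copes. For H1a this is largely right: the mixed model uses data collected before removal, and pattern-mixture models are planned. A reader might infer that the primary analysis drops TOMM failures; the documents say nothing of the kind. For work/school the reply fails, although any dropout before discharge leaves the same gap and this rule only adds to it.

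A third reply concerns recruitment. A reader might infer that only about 88 would be randomised (200 × 0.49 × 0.90). The documents do not support that: recruitment continues to a target of 98, the figure of 200 is only anticipated, and a baseline failure has no interpretable evidence of impairment and could reasonably be handled like others who do not qualify. What remains is that the replacement wording does not say so.

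**Conclusion.** The point holds as a minor one, with medium confidence. The rule as written permits removal of randomised participants on a post-treatment measure and ends follow-up that its own reason does not touch. It would be too strong to say the plan intends this, or that its power figures are wrong; they reproduce.

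The size cannot be established from the documents. Under the assumed failure rates about 6-14 of 98 would be affected, and the illustrative bias is about 0.05 SD or less, against planned effect sizes of 0.72 (H1a) and 0.64 (H1b). Bias is near zero if failure rates and mechanisms match between arms. These results depend on the assumed 2-5% per visit, the failure mechanisms and the correlation r. No claim is made about self-report scores from a low-effort session, because the documents do not say whether they remain usable.

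The gap in the eligibility and replacement wording holds under either reading. Its likely cost is more baseline testing, roughly 218-251 people in place of 200 on the assumptions shown, unless the 200 already allows for it. The target of 98 need not be missed.

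**What to change.** - Reconcile Study Measures, Table 3 and Section 9.8 by stating that the TOMM exclusion is an eligibility check at the baseline assessment, before randomisation.
- Add it to the eligibility lists in Sections 9 and 10, cover it in the replacement rule, and say whether the 200 to be tested allows for it.
- State that a TOMM failure after randomisation neither ends outcome collection (later visits, monthly calls, medical-record data) nor removes the participant from any analysis.
- Prespecify whether the performance-based scores from a failed visit (global deficit score, UPSA-B) are kept or set to missing, with the other choice as a sensitivity analysis.
- Whether study treatment continues after such a failure is for the authors to reconcile; no rule is proposed here.

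The cost is wording in the protocol and analysis plan. The downsides are that a few low-effort scores remain in one of the two analyses, and somewhat more people may need baseline testing.

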Our research design purposely includes all Aspire Center residents with cognitive impairment. We recognize that the etiologies of such impairment may differ between individuals, but we are taking a trans-diagnostic approach in this practical clinical trial so the results will be as generalizable as possible to the population of homeless, treatment-seeking O/O/O Veterans with mental health conditions and cognitive impairment. In keeping with our pragmatic goals, we chose not to restrict the sample with regard to types of mental health conditions, types of cognitive impairment, types of medications, and so on. These factors may affect the cognitive profiles of the participants, as well as their response to CCT, however, our first goal in this pilot trial in a new population is to see if CCT works; thus, our primary goal is to examine efficacy broadly. If the randomized groups differ with regard to mental health conditions, types or level of cognitive impairment, types of medications, and so on, we will take those differences into account in our analyses, and we will additionally examine moderators of treatment outcome. With regard to the control group, we considered a wait-list control group, but rejected that option because it does not control for therapist time and attention, may introduce cohort effects, and would be impractical in a residential setting where participants in the wait-list group could be discharged before they were able to participate in CCT. We also considered a treatment as usual control group, but rejected that option because it does not control for therapist time and attention. Therefore, we designed the Holistic Cognitive Education control group that will control for these potential confounds.

Quality Assurance

The PI will train and supervise the research staff collecting data via observation of the assessment sessions of the first 10 subjects enrolled and further observation of one session every three months. Protocol adherence will be enhanced by means of an electronic calendar to track participant enrollment, assessment, and discharge dates, as well as to project dates for the monthly post-discharge calls. Treatment fidelity will be carefully monitored with procedures described above.

Data Management and Information Security

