Electronic data will be stored on a secure research drive on our VA network, accessible only to VA research personnel associated with the proposed study. Electronic records will include a password-protected key linking subject numbers with subject names. Paper records will be coded by subject number only, and will not include participant names, with the exception of consent forms, which will be stored separately and will include names, but no subject numbers. All paper records will be kept in locked cabinets in a locked room. A custom-tailored database system will be developed for this project to ensure the highest possible data reliability. Data entry programs will include double data entry, item prompts, skip patterns, range checks, and logical validity routines. Consultation regarding data management and information security issues will be provided by [name], with whom [name] has worked for over 10 years.

Analytic Plan and Power Analyses

Data analyses will proceed in stages, with [name] serving as a statistical consultant during the award period. At first, descriptive statistics and exploratory graphing will be used to assess the normality of the data in terms of the presence of skewness and/or outliers. The continuous outcome data will be transformed if necessary by using an appropriate transformation such as the log transformation for skewed long tailed data. We will check to ensure that the randomization worked and there are no significant differences between the experimental and control groups on demographics, clinical characteristics, and/or baseline cognition/functional

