Dependent variables: Proportion of months housed, proportion of months engaged in productive activity (work or school), and proportion of VA healthcare appointments attended during the 1-year follow up period (all three outcomes based on monthly data collected during the 1-year follow-up period). Any missing data on housing and work/school status will be accounted for by using a proportion based on the available data points. Healthcare appointment attendance will be gathered from CPRS data and will not be subject to missing data.

Independent variable: Treatment group (CCT vs education control).

Statistical analyses: ANOVA models comparing the treatment and control group on the three dependent variables above. We have selected ANOVA over alternative models (t-test; Wilcoxon Rank Sum; Poisson regression) due to the type of dependent variables (continuous) and the option to include any covariates that might be imbalanced between the treatment groups.

Power analysis: With 78 subjects (39 subjects per group), we will have .80 power to detect an effect size of .64, a medium-to-large effect size.

capacity, disability, and community reintegration.

Dependent variables: UPSA-B at 15 weeks, WHODAS 2.0 at 15 weeks, proportion of months housed, proportion of months engaged in productive activity (work or school), and proportion of VA healthcare appointments attended during the 1-year follow up period.

Independent variables: Treatment group (CCT vs education control).

Mediators: Cognitive improvement in GDS composite from 0-10 weeks (slope of change across weeks), improvement in CPSA cognitive strategy use from 0-10 weeks (slope of change across weeks).

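### Covariates enter the confirmatory analyses only if the randomised groups happen to differ; a short list fixed in advance, above all for the H1b ANOVA, would remove analyst discretion and may gain precision.

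*Combined protocol and SAP*

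**What the plan says.** All passages are in Section 9 of the combined protocol and SAP.

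- **Design Considerations.** "If the randomized groups differ with regard to mental health conditions, types or level of cognitive impairment, types of medications, and so on", then "we will take those differences into account in our analyses". No threshold or closed list is given, and the form of adjustment is not stated.
- **Analytic Plan and Power Analyses.** "We will check to ensure that the randomization worked and there are no significant differences between the experimental and control groups", on demographics, clinical characteristics and baseline cognition and function. The text breaks off in this sentence and resumes within the description of the mixed model, so whatever followed cannot be read.
- **H1b, statistical analyses.** ANOVA is preferred to other methods partly for "the option to include any covariates that might be imbalanced between the treatment groups". The only independent variable listed is treatment group.
- **Paragraph after the exclusion criteria.** "In the unlikely event in a study this size that the treatment groups differ in this regard, alcohol history may be used as a covariate".
- **H1a.** The independent variables are treatment group and time at 0, 5, 10 and 15 weeks, in a saturated treatment-by-time mixed model. Week 0 is therefore one of the modelled responses.
- **Table 2 (intake measures).** The Residential Timeline Follow-Back records "Residential history (number of days homeless, unstably housed, in an institution, or housed in the past 6 months"). It is collected on everyone at intake but is not a term in the H1b model.
- **Exploratory Aim 3.** PTSD, depression, substance abuse history, TBI, duration of homelessness and baseline GDS are entered in the H1a and H1b models as moderators, to assess interactions with treatment.

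**The concern.** Adjusting for a baseline variable helps when that variable predicts the outcome. Whether the arms differ on it is a separate question, and in a randomised trial any difference is chance. Choosing covariates by imbalance therefore uses the wrong criterion: it can bring in variables unrelated to outcome and leave out predictive ones that happen to be balanced.

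Two things are at stake. The first is precision in H1b, where the visible plan fixes no baseline term. The second is discretion. Wording that makes adjustment optional, over an open-ended list, leaves the model behind each H1b p-value undetermined until the data are in hand.

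**Working it through.** **Inputs from the plan.** H1b: 39 per group, power .80, effect size .64. H1a: effect size .72, correlation .5 between time points. Alpha: Bonferroni per outcome domain for H1a and H1b.

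**Assumptions.** The base alpha is .05 two-sided, and Bonferroni over the three H1b outcomes gives .05/3 = .0167. The plan states neither the base alpha nor the divisor. It gives no correlation between any baseline variable and an H1b outcome, so r = .1 to .5 is an assumed range.

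**Step 1: reproduce the stated H1b power.** The noncentrality is d × √(n/2) = .64 × √19.5 = 2.826. With 76 degrees of freedom and critical value 1.992, the noncentral t gives power .797. The stated .80 is reproduced, at uncorrected .05. At .0167 (critical value 2.448) power is .648.

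**Step 2: add one prespecified covariate.** The residual variance becomes 1 − r², the noncentrality becomes .64 × √19.5 / √(1 − r²), and the degrees of freedom fall to 75.

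| Assumed r | 1 − r² | Noncentrality | Power, alpha .05 | Power, alpha .05/3 |
|---|---|---|---|---|
| none | 1.00 | 2.826 | .80 | .65 |
| .1 | .99 | 2.840 | .80 | .65 |
| .2 | .96 | 2.884 | .81 | .67 |
| .3 | .91 | 2.963 | .83 | .70 |
| .5 | .75 | 3.263 | .90 | .79 |

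The effect detectable with .80 power at alpha .05 falls from .64 to .61 (r = .3) or .56 (r = .5). The formula ignores the small loss from chance covariate imbalance; the simulation in step 3 includes it and agrees to within .01.

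**Step 3: does adjusting only when the arms differ recover the gain?** This was simulated with 100,000 trials per setting, 39 per arm, one covariate, and adjustment only when the covariate differs at p < .05.

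| Assumed r | Power, always adjust | Power, adjust if different | Type I error, adjust if different |
|---|---|---|---|
| .3 | .83 | .80 | 4.7% |
| .5 | .89 | .81 | 4.3% |

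At r = .7 the type I error of the conditional rule is 3.7%. The rule recovers little of the gain, and applied mechanically it is slightly conservative. Error rises above 5% only if the analyst reports whichever of the adjusted and unadjusted results is significant: 6.3%, 7.2% and 8.3% at r = .3, .5 and .7.

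**Step 4: how easily could the trigger fire?** If k independent baseline variables were each tested at .05, the chance of at least one significant difference is 1 − .95^k: 23% for k = 5, 40% for 10 and 54% for 15. The plan gives neither k nor a threshold, and these measures are unlikely to be independent, so this is only an illustration.

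**Step 5: H1a.** Take a single follow-up, the stated correlation ρ = .5, 39 per arm, d = .72 and an assumed alpha of .025 (.05 over the two co-primary outcomes).

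- Change from baseline: relative variance 2(1 − ρ) = 1.00, power .83 (normal approximation).
- Baseline as a covariate, or week-0 means constrained equal: relative variance 1 − ρ² = .75, power .92.

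Baseline is thus already in the H1a model, but a saturated model read as change from week 0 does not use it fully.

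**The case against.** The other side has several good points.

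- **H1a already uses baseline.** A reader might infer that prognostic baselines go unused in both H1a and H1b. For H1a that is not so: each outcome's own baseline is the week-0 response. Only the handling of week 0 is open to improvement.
- **No visible sentence states a complete test-then-adjust rule.** A reader might infer one rule repeated throughout. Design Considerations has an adjustment clause without a test, the Analytic Plan has a check without a visible consequence, and the H1b and alcohol-history wording is permissive. The text after the check is lost, so it cannot be said that no covariate rule stood there.
- **The predictors are not shown to be strong.** Design Considerations says only that such factors may affect cognitive profiles and response to CCT. Every participant must be homeless or unstably housed at entry, which may narrow the range of residential history. At r = .1 or .2 the gain is negligible.
- **Type I error.** A reader might infer that the conditional rule inflates it. Step 3 shows that it does not. Inflation needs a choice between results after seeing them, which the plan does not propose.
- **Aim 3 names several baselines in advance.** It does, but as exploratory interaction terms, which do not fix the confirmatory model.

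These points narrow the concern. What remains is that every visible covariate provision for the confirmatory analyses depends on imbalance, and that H1b's stated model contains treatment group alone.

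**Conclusion.** The point holds as an improvement to the analysis plan, mainly for H1b. In the visible text, adjustment is triggered by chance imbalance and left partly to the analyst, while a natural baseline for months housed is collected and not used. The consequence is discretion plus possible loss of precision; the documents do not support a claim of an invalid test or of inflated error under the rule as written.

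The size depends on an assumed correlation. At d = .64 and alpha .05, power rises from .80 to between .80 and .90 for r from .1 to .5. At an assumed .05/3 it rises from .65 to between .65 and .79. The gain matters only if the covariate is at least moderately correlated with the outcome; below about .2 there is little. The case for fixing the model in advance does not depend on that gain. For H1a the change is a refinement, with the .83 and .92 figures illustrative of a single follow-up.

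**What to change.** 1. Replace imbalance-triggered adjustment in Design Considerations, the H1b paragraph and the alcohol-history remark with one short covariate list per outcome, fixed before outcome data are seen by arm.
2. **H1b.** Include at least intake residential history in the model for proportion of months housed. For work or school and for appointment attendance, include a baseline counterpart where one is collected. The text on subject characterisation mentions vocational history at intake, but Table 2 as readable lists no instrument for it, so confirm that it is available. No baseline measure of attendance is listed.
3. **H1a.** State how week 0 is handled: constrain the week-0 means to be equal between arms, or move baseline to the covariate side, in place of reading the saturated model as change from baseline.
4. Present baseline tables descriptively, without significance tests. Keep adjustment for observed imbalances, including alcohol history, for sensitivity analyses labelled as such.

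**Cost.** SAP wording and one or two degrees of freedom per model. Residential history is already collected. If its correlation with later housing proves below about .2, little precision is gained, but the model is still fixed in advance.
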